#### 7.3.1.5. Exploratory Efficacy Analyses

Exploratory analyses of the effect of ADAs on the efficacy of SBC-102 may be explored using stratified analyses on efficacy endpoints.

Observed values and changes and percent changes from baseline in other exploratory efficacy endpoints may be tabulated for each evaluation time point. These will include changes in

liver and spleen size/volume, as measured by ultrasound or magnetic resonance imaging (MRI). Liver and spleen volumes will be presented in statistical outputs as multiples of normal (where normal is defined as 2.5% of body weight for liver and 0.2% of body weight for spleen); changes will be calculated if the same method was used at baseline and the post-baseline time point;

Shift tables may be used to tabulate dietary changes, including shift from low-cholesterol diet to unrestricted diet if sufficient data exist for summary.

# 7.4. Pharmacokinetic Analyses

#### 7.4.1. Plasma Concentration Analysis

Plasma concentrations will be summarized by time point and by visit. The summaries will include mean, standard deviation, geometric mean and standard deviation, median, min, max and geometric CV%. Graphical displays and listings will also be created.

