1.4.1 Completed Study LAL-CL01

LAL-CL01, the first clinical study with sebelipase alfa, evaluated the safety, tolerability, and pharmacokinetics (PK) of sebelipase alfa following a 4-week regimen of once-weekly (qw) IV infusions of sebelipase alfa at doses of 0.35 mg/kg, 1 mg/kg, and 3 mg/kg in adult subjects with liver dysfunction due to LAL Deficiency. A total of 9 subjects were enrolled into 3 sequential cohorts of 3 subjects each.

All 3 doses of sebelipase alfa were well tolerated by the subjects in this study. There were no deaths or treatment-emergent serious adverse events (SAEs), and no subject experienced an infusion-associated reaction (IAR) or discontinued treatment due to a treatment-emergent adverse event (TEAE). Most (86.4%) of the 44 reported TEAEs were considered unrelated to sebelipase alfa, and all but one were assessed by the Investigator as Grade 1 (86.4%) or Grade 2 (11.4%) in severity. One subject in the 3 mg/kg dose cohort had a Grade 4 TEAE of hypercholesterolemia. Although the subject was asymptomatic, this laboratory abnormality met the definition of a Grade 4 event according to Common Terminology Criteria for Adverse Events, which was used to assess severity in this study.

All 3 doses of sebelipase alfa were biologically active, as evidenced by decreases in alanine aminotransferase (ALT) and aspartate aminotransferase (AST) and increases in serum lipids (total cholesterol, triglycerides, and LDL cholesterol), which were observed within 2 and 4 weeks, respectively, and were reversible following discontinuation of sebelipase alfa therapy. Effects on serum lipids appeared more pronounced in the 3 mg/kg dose cohort, whereas effects on ALT and AST appeared to be independent of dose.

PK data in adult subjects with LAL Deficiency indicate that sebelipase alfa has a short plasma half-life, ranging from 0.07 to 2.04 hours at the lowest dose of 0.35 mg/kg and from 0.09 to 0.21 hours at higher doses of 1 or 3 mg/kg. Sebelipase alfa area under the concentration-time curve (AUC) and maximum observed concentration (C_{max}) increased proportional to dose from 0.35 to 1 mg/kg and more than proportional to dose from 1 to 3 mg/kg. Clinical PK data for sebelipase alfa are not yet available for children and adolescents with LAL Deficiency.

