2.2 Secondary Objectives

The secondary objectives are:

- To evaluate the effects of sebelipase alfa on:
- Survival at 12 months of age
- Survival past 12 months of age
- Growth parameters
- Hepatomegaly, splenomegaly, and liver function
- Hematological parameters
- To characterize the PK of sebelipase alfa delivered by IV infusion

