5.1.14 Pharmacokinetic Assessments

Sampling for measurement of sebelipase alfa serum levels will be performed during the study visits indicated in Appendix A. A sparse sampling scheme will be employed for to reduce the risk of iatrogenic anemia. Up to 3 blood samples will be collected at each study visit requiring a PK assessment. These samples will be collected within broad time windows, rather than at discrete time points, to allow more flexibility in the management of PK sampling for these subjects and to provide opportunities for measurement of drug concentrations across a broader time period with limited sampling:

In all subjects:

• Between 0 hour to end of infusion (i.e. when the infusion bag has been emptied, but prior to the sodium chloride flush)

In those subjects for whom the thresholds for allowed blood collection volumes have not been exceeded: One sample will be obtained during the following time windows:

- 0 to 30 minutes after completion of the infusion
- 0.5 to 1 hour after completion of the infusion

PK samples should not be taken from the same extremity where the infusion catheter is in place. All PK samples, at time points that coincide with a vital sign assessment, will be taken before cuff inflation for blood pressure assessment on the non-infusion arm. PK samples at other time points will be taken at least 5 minutes after cuff deflation.

Refer to the SOM and/or laboratory manual for further details regarding the collection, processing, and storage of these samples.

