8.9 Pharmacokinetics

Pharmacokinetics will be analyzed for the PK Analysis Set. C_{max} will be recorded from direct observation. C_{max} will be summarized by dose of sebelipase alfa, if applicable.

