# 4.1. Changes from Analyses Specified in the Protocol

Protocol Section 4.5 defines a concomitant medication as a medication starting or ongoing at the time of the signing of the informed consent. However, concomitant medications will be defined relative to the first dose of sebelipase alpha.

In the protocol, an exploratory objective is to evaluate potential disease-related biomarkers. Biomarker samples are stored for future analysis and will not be analyzed for this analysis plan.

The protocol mentions pharmacokinetic analysis is a secondary objective and will be done by IV infusion. PK analysis will not be analyzed as part of this analysis plan.

No formal inferential statistical testing will be performed.

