#### 7.4.2. PK Analysis

Only serum sebelipase alfa concentration will be summarized and presented in listings. No other analysis is planned.

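### The SAP summarizes serum concentrations without a dose factor and drops the protocol's Cmax by dose, so no planned summary answers the secondary PK objective

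*SAP*

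**What the plan says.** Protocol 2.2 lists among the secondary objectives "To characterize the PK of sebelipase alfa delivered by IV infusion". Protocol 8.9 takes Cmax directly from the observed values and says that it "will be summarized by dose of sebelipase alfa, if applicable". The commitment is conditional. The synopsis makes Cmax depend on the available data, Section 3.2.2.3 on blood volume, and Table 2 puts PK samples in the optional third tier.

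The SAP treats PK in four places:

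- Section 4.1, which lists changes from the protocol: "PK analysis will not be analyzed as part of this analysis plan".
- Section 5.3 repeats the sampling windows and limits the analysis to concentrations.
- Section 7.4.1: "Plasma concentrations will be summarized by time point and by visit", with arithmetic and geometric summaries, geometric CV, graphs and listings.
- Section 7.4.2: "Only serum sebelipase alfa concentration will be summarized and presented in listings. No other analysis is planned".

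Dose appears elsewhere in the SAP. Section 7 puts the associated dose on every subject listing, and Section 7.2.1 summarizes exposure by dose and overall. Section 7.5 plans no subgroup analysis.

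Under protocol 3.1 and 3.1.1, all subjects start at 1 mg/kg weekly. Those who meet criteria may go to 3 mg/kg and, case by case, up to 5 mg/kg. Appendix A places PK samples at Week 0, at one visit in the Week 17 to 24 block (the exact column is unclear in the extracted table) and at Week 48.

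**The concern.** Two things are lost between protocol and SAP: the parameter (Cmax) and the stratifier (dose). A programmer who follows SAP 7.4.1 to the letter produces one geometric mean and one CV per window and visit, whatever doses the subjects are on. After Week 0 such a number need not describe exposure at any dose that was given. The adult study gives a specific reason for care, since AUC and Cmax rose "more than proportional to dose from 1 to 3 mg/kg" (protocol 1.4.1).

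SAP 4.1 adds uncertainty about what will be produced at all. Read literally, it removes PK, whereas 5.3 and 7.4 still plan tables and graphs. It gives no reason, does not say that Cmax by dose is the item dropped, and names no other report. Without Cmax, the protocol's exploratory look at the effect of anti-drug antibodies on Cmax (3.2.2.3) also has no planned summary.

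**Working it through.** The documents state no PK sample size, precision or test, so there is no figure to reproduce. The check asks where doses can mix and how much that changes the planned statistics.

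**Where mixing can occur.** At Week 0 all subjects receive 1 mg/kg, so there is none. At the mid-study PK visit and at Week 48, escalation may already have taken place.

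**Size of the dose mix.** Let R be the ratio of exposure at 3 mg/kg to that at 1 mg/kg, and p the share of subjects on 3 mg/kg. If subjects do not vary within a dose:

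- pooled geometric mean relative to 1 mg/kg = R^p
- variance of log concentration = p(1 − p)(ln R)²
- geometric CV = √(exp(variance) − 1)

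R = 3 is dose proportionality, which is conservative given the adult result. The documents give no split, so p = 0.5 is an assumption.

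- Geometric mean ratio: 3^0.5 = 1.73
- Variance: 0.25 × (ln 3)² = 0.25 × 1.207 = 0.302
- Geometric CV: √(exp(0.302) − 1) = √0.352 = 59%

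**Sensitivity to R.** The documents say more than proportional but give no ratio. The assumed values R = 5 and R = 10, with p = 0.5, give geometric mean ratios of 2.24 and 3.16 and CVs of 95% and 166%. They only show the direction.

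**Sensitivity to the split and to within-dose spread.** For ten subjects under proportionality, an assumed within-dose geometric CV w adds ln(1 + w²) to the variance:

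| Subjects on 1 / 3 / 5 mg/kg | Pooled geometric mean relative to 1 mg/kg | Pooled CV, w = 30% | Pooled CV, w = 50% |
|---|---|---|---|
| 10 / 0 / 0 | 1.00 | 30% | 50% |
| 8 / 2 / 0 | 1.25 | 56.8% | 71.9% |
| 5 / 5 / 0 | 1.73 | 68.8% | 83.1% |
| 2 / 8 / 0 | 2.41 | 56.8% | 71.9% |
| 4 / 4 / 2 | 2.14 | 81.3% | 95.1% |
| 2 / 5 / 3 | 2.81 | 70.3% | 84.5% |

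With dose as a stratum, the CV returns to the assumed 30% or 50%.

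**Sampling time, a separate matter.** One protocol window is "0 to 30 minutes after completion of the infusion". At the adult half-lives for 1 or 3 mg/kg (0.09 to 0.21 h, protocol 1.4.1), a mono-exponential fall over 0.5 h is 2^(0.5/0.21) = 5.2-fold to 2^(0.5/0.09) = 47-fold. If draw times are uniform over the window, the SD of log concentration is (ln 2 / half-life) × 0.5/√12, or 0.476 to 1.112. The resulting geometric CV is about 50% to 156% from timing alone. Stratifying by dose does not remove this spread; showing actual times makes it visible.

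**The case against.** The strongest defence is that little information is lost. At most about ten infants are expected, PK visits are few, and every listing shows the dose, so a reader can find the highest concentration by dose by hand. That stands. A reader might infer that the PK objective cannot be answered. The documents do not support this; what is missing is a planned summary.

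Nor does the SAP say that it pools 1, 3 and 5 mg/kg. Pooling follows from its silence, cannot happen at Week 0, and involves 5 mg/kg only if case-by-case escalation occurs. Protocol 1.5.1 does not expect to need doses above 3 mg/kg unless efficacy is lost to neutralizing antibodies.

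The change is declared in SAP 4.1, so it would be wrong to call it hidden. One coherent reading is that 4.1 drops PK parameters and keeps concentrations, but the text does not say so. The protocol's own commitment is also conditional. That excuses sparse results, but not a plan with no by-dose summary when data exist.

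A reader might also blame the SAP for the wide windows. They come from protocol 5.1.14, which chose them for flexibility alongside sparse sampling to limit iatrogenic anemia, and the SAP copies them. Finally, splitting ten subjects by dose, visit and window may leave cells too small for a useful geometric CV. This is a fair limit on any remedy.

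**Conclusion.** The point holds. The SAP omits the protocol's observed Cmax by dose, gives its concentration tables no dose factor, and contradicts itself on whether PK is analysed. No planned summary answers the secondary PK objective, although the listings would allow an answer to be derived.

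For later PK visits, the figures to carry forward are a pooled geometric mean about 1.7 times the 1 mg/kg value and a geometric CV of about 59% from dose mix alone. They rest on an assumed 50/50 split of 1 and 3 mg/kg, proportional exposure and no within-dose spread. Greater-than-proportional exposure would enlarge both, but the documents do not say by how much, so the results for R = 5 and R = 10 should not be quoted as expected values. The fall within the sampling window rests on adult half-lives; the protocol gives no half-life for infants. The study is descriptive with a primary safety objective, so this concerns the usefulness and clarity of a secondary analysis and leaves the main conclusions untouched.

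**What to change.** 1. In SAP 7.4, summarize concentrations and observed Cmax by the dose received at that infusion, within visit where numbers allow. Define Cmax as the highest observed concentration at that infusion and report its actual time. This agrees with protocol 8.9 and the SAP's own abbreviation list; tying Cmax to one nominal sample would change the endpoint.
2. Where a cell is very small, show individual values instead of a geometric mean and CV.
3. Plot and list concentrations by actual time relative to the end of infusion, labelled by dose.
4. Keep the disclosure in SAP 4.1 but reword it to state exactly which PK analyses are dropped, or where they will be reported, consistently with 5.3 and 7.4. Use one term for the matrix: 7.4.1 says plasma, while 5.3 and 7.4.2 say serum.

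The cost is SAP wording and one more stratifier in the programming, with no extra blood. The downside is small n per dose cell, which item 2 addresses.

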#### 7.4.2. PK Analysis

Only serum sebelipase alfa concentration will be summarized and presented in listings. No other analysis is planned.

# 7.5. Subgroup Analysis

No subgroup analysis is planned.

# 7.6. Additional Exploratory Analyses

Post-hoc subgroup analyses may be performed as needed. No planned exploratory analysis is planned at this time.

#### 7.7. Interim Analyses

No formal interim analysis is planned. Analyses are descriptive and no adjustments will be made for multiple comparisons.

# 7.8. Data Monitoring Committee

An independent Safety Review Committee (SRC) will perform periodic reviews of aggregated safety data for study LAL-CL08 on an at least semiannual basis (i.e., every 6 months) from the date of enrollment of the first patient until completion of dosing for all patients in the study. Details of SRC procedures, processes and analysis for the study are provided in an SRC Charter.

# 9 APPENDICES

# 9.1 Protocol Schedule of events

Refer to the approved study protocol for a schedule of events.

# 9.2 Changes from Analyses Specified in the Previous Version of the SAP

Not applicable

# 9.3 Sample Size, Power, and Randomization

No formal sample size calculations were performed for this study; the projected enrollment is based on feasibility. Given the rarity of LAL-D, it is not expected that more than 10 patients will be treated.

# 9.4 Technical Specifications for Derived Variables

#### 9.4.1 Age

Age will be presented as the number of years between date of birth and the reference date. The following age will be computed, with reference dates indicated:

#### Table 3: Age and reference date

AGE	REFERENCE DATE	
Age at Enrollment	Date of Signing ICF	
Age at First Dose of SBC-102	Date of First Dose of SBC-102	

In cases where only the month and year are provided for a date, the day for the date will be imputed as 15. Missing month will be imputed as June. In cases where the day is observed but the month is missing, the date will be imputed as July 1.

#### 9.4.2 Time to Death (from Birth)

Time to Death (months) = [(Date of Death - Date of Birth + 1)/365.25]\*12;

This derived variable will be used in the calculation of Kaplan-Meier estimate of median age at death/median survival since birth. This calculation will be adjusted for subjects born prematurely; details are described in Section 7.3.1.4.

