8.1 General Considerations

All data will be presented in listings; summary tables and graphs will be provided, as appropriate. Unless otherwise noted, tabulations for efficacy endpoints will be presented for subjects in the Full Analysis Set (FAS). Descriptive summary statistics (n, mean, median, standard deviation, minimum and maximum) will be calculated for the continuous variables. Shift tables and/or frequencies and percentages will be produced for the categorical variables. When percentages are reported, the number of treated subjects will be used as the denominator, unless otherwise noted. As appropriate, 95% two-sided confidence intervals (CIs) will be calculated around the estimates based on the exact binomial distribution for binomial endpoints and the t-distribution for continuous endpoints.

Baseline will be defined as the last measurement prior to the first infusion of sebelipase alfa. (Note: For exploratory analyses, the first available measurement after initiation of treatment may be used as baseline if a pretreatment measurement is unavailable.) In order to facilitate comparison with literature, survival analyses will be presented with subject birth date as "time 0"; analyses of other endpoints over time will consider date of first dose as "time 0".

Details of the planned analyses and statistical methodologies will be provided in a separate Statistical Analysis Plan.

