#### 7.3.1.1. Overall Survival and Survival at 12, 18, 24 and 36 months of age

Survival will be analyzed as the proportion of subjects surviving to 12, 18, 24, and 36 months of age. A 95% exact confidence interval, calculated using the Clopper-Pearson method, will also be presented for each proportion estimate. In addition, the Kaplan-Meier estimate of median survival time and 95% confidence interval will be summarized as well as the number of deaths and the number and percentage of subjects censored. Kaplan-Meier curves of survival since birth and survival since first dose of SBC-102 will be presented. Kaplan-Meier estimates of median survival since first dose of SBC-102 will also be provided, along with 95% CIs, if estimable.

Survival rates and median age at death derived from this study will be compared to rates/times reported in the literature and previous studies. No statistical comparisons will be performed.

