#### 7.3.1.4. Anthropometric Parameters

Anthropometric indicators of growth will be plotted on standard growth curves. Z-scores and percentiles based on the age-gender standardized norms will be calculated in accordance with the methodology described by the WHO (subjects  $\leq 24$  months) or CDC (subjects > 24 months to 18 years) and using the growth charts relevant to the respective methodology. Summaries will include summaries of observed z-scores and percentiles at each visit and also the change from baseline and the percentage change from baseline (percentile data only). In addition, the percentages of subjects who meet criteria for underweight (<-2 standard deviations [SD] from the median for WFA), stunting (<-2 SD from the median for LFA/HFA), and wasting (<-2 SD from the median for WFL/WFH) will be tabulated for each time point.

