#### 9.4.12.6 Denver II Developmental Screening Test (DDST)

The Denver II Developmental Screening Test (DDST) will be administered at the time points specified in the schedule of assessments.

The test is a standardized measure to assess development in children from 1 month to 6 years of age (Frankenberg et al., 1992). It includes performance-based and parent-reported items in 4 functional areas: fine motor-adaptive, gross motor, personal-social, and language skills with respect to the age-matched population. The test was normed on a diverse sample of children who were full term and had no obvious developmental disabilities; the norms indicate when 25%, 50%, 75%, and 90% of children passed each item. DDST II results are expressed as Normal, Abnormal, Questionable, and Untestable. The instrument has good inter-rater and test-retest reliability (correlations  $\geq$  0.90 for most tests).

The test must be administered by a trained clinician. Administration and scoring of DDST is based upon the child's age. (Note that for premature infants, the number of months premature is subtracted from the infant's chronological age.) For each test item administered, the clinician determines if the child's response falls within or outside of the normal expected range of success on that item for the child's age. The interpretation of the individual test items is then used to classify the child's development in each functional area and for the overall test.

Refer to the Study Operations Manual (SOM) for further information on administration and scoring of DDST.

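### SAP 9.4.2 announces an undefined prematurity adjustment to time from birth to death, through a cross-reference that leads nowhere, and this conflicts with birth date as the survival time origin

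*SAP*

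**What the plan says.** Protocol 8.1 states that "survival analyses will be presented with subject birth date as" time 0, and gives ease of comparison with the literature as the reason.

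SAP 7.3.1.1 carries this forward: "Survival will be analyzed as the proportion of subjects surviving to 12, 18, 24, and 36 months of age". It also plans Kaplan-Meier curves starting at birth and at first dose, and adds: "Survival rates and median age at death derived from this study will be compared to rates/times reported in the literature and previous studies". It mentions no prematurity correction.

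SAP 9.4.2 defines the variable behind the birth-origin curve and the median age at death. The printed formula is "Date of Death - Date of Birth + 1)/365.25", multiplied by 12 to give months. The section then says: "This calculation will be adjusted for subjects born prematurely; details are described in Section 7.3.1.4".

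The section it points to, SAP 7.3.1.4, is about anthropometry: "Z-scores and percentiles based on the age-gender standardized norms will be calculated in accordance with the methodology described by the WHO". It says nothing about prematurity, gestational age or survival.

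The only prematurity rule in the SAP is in 9.4.12.6, for the Denver II: "for premature infants, the number of months premature is subtracted from the" chronological age. SAP 9.4.1 defines age chronologically: "Age will be presented as the number of years between date of birth and the reference date".

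**The concern.** Time lived since birth is the same quantity for a term and a preterm child. Correcting for prematurity makes sense when a child is compared with developmental norms. It has no place on a survival clock whose origin is the date of birth.

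The sentence therefore causes two problems. It instructs the programmer to apply a rule that does not exist, so size, direction and the handling of censored children would be decided at programming, in an open-label study of at most 10 children. And whatever rule is chosen, the Kaplan-Meier variable stops being time since birth while the milestone proportions remain ages since birth.

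Survival at 12 months of age and survival past 12 months of age are the first secondary objectives in Protocol 2.2, and the survival results are the ones to be set against the literature. Protocol 1.1.2 describes the disease as usually fatal within the first 6 months of life, so a shift of one or two months would be large on that scale.

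**Working it through.** The plan states no figure to reproduce. The check traces the rule and then sizes it under a stated assumption.

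**1. Tracing the rule**

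- SAP 9.4.2: adjustment announced, details deferred to 7.3.1.4.
- SAP 7.3.1.4: WHO and CDC z-scores, percentiles and growth status only.
- SAP 4.1 (changes from the protocol): the adjustment is not listed.
- SAP 9.4.3 (time from first infusion to death): no adjustment. For a preterm child who dies, age at first dose plus survival since first dose would no longer match survival since birth.
- Censoring: SAP 9.4.2 speaks only of time to death. If only deaths were shifted, deaths and censored children would be on different clocks.
- Data: Protocol 5.1.4 does not name gestational age among the demographic items, although Protocol 5.1.3 records birth history.

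The conflict with the birth-date origin does not depend on the direction of the adjustment.

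**2. Size of the shift**

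Assumption: the adjustment subtracts the time premature, as for the Denver II. Shift in months = weeks × 7 / 365.25 × 12.

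| Weeks early | Shift (months) | Death at 13.0 months becomes |
|---|---|---|
| 4 | 0.92 | 12.08 |
| 8 | 1.84 | 11.16 |
| 10 | 2.30 | 10.70 |

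So a child born 8 weeks early who dies at 13.0 months counts as a 12-month survivor in the milestone proportion and as a death before 12 months on the curve.

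**3. Effect on survival at 12 months (invented cohort)**

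Ten children: deaths at 4, 7 and 12.5 months, seven followed to 36 months. The third death is the preterm child. (Day 380 in the SAP formula: 381 / 365.25 × 12 = 12.5.)

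- Chronological: S(12) = 9/10 × 8/9 = 80%. This equals the milestone proportion, 8/10 (95% Clopper-Pearson CI 44.4% to 97.5%).
- Shifted by 0.92, 1.84 or 2.30 months, the third death falls at 11.58, 10.66 or 10.20 months. In each case S(12) = 9/10 × 8/9 × 7/8 = 70%, while the milestone proportion stays at 80%.

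**4. Effect on the median (invented cohort)**

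Ten children: deaths at 3, 4, 5, 7 and 12.5 months, the fifth preterm, and five followed to 36 months. Take the median as the first time at which the curve is at or below 50%. It moves from 12.5 to 11.58, 10.66 or 10.20 months.

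**5. When nothing changes at 12 months**

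- No preterm child is enrolled.
- In the cohort of step 3, the only preterm child is instead one followed to 36 months: S(12) is 80% either way.
- Deaths at 4 and 7 months only, the second in a child born 8 weeks early: 7 − 1.84 = 5.2 months. S(12) is 80% either way, although S(6) falls from 90% to 80%.

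**The case against.** The strongest reply is that the text does not say what the adjustment is. The printed formula contains no subtraction, and the sentence may be a note about growth age that ended up in the wrong section. A reader might infer that the SAP shortens survival time for preterm infants. The documents do not say so: that reading borrows the Denver II rule. This stands, and the subtraction figures above are therefore an assumption.

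Second, the reach is narrow. Protocol 8.7 analyses survival as milestone proportions and calls Kaplan-Meier complementary. The milestone proportions and survival since first dose carry no stated adjustment. Survival is a secondary, descriptive analysis, SAP 7.3.1.1 rules out statistical comparison with the literature, and deaths are listed individually, so a discrepancy could be seen. This also stands and limits the severity.

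Neither reply rescues the sentence. A misplaced note should be removed, and an intended adjustment needs a rule and has to be reconciled with the protocol's time origin.

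**Conclusion.** The point holds as an unspecified instruction that conflicts with the protocol. SAP 9.4.2 cannot be carried out as written, and any non-zero adjustment contradicts birth date as time 0. The exposed outputs are the birth-origin Kaplan-Meier curve and the median age at death. This should be fixed, but it does not undermine the study.

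Under the subtraction assumption the shift is 0.92 to 2.30 months for birth 4 to 10 weeks early. One child can open a gap of 10 percentage points between the curve and the milestone proportion when 10 children are treated and none is censored before the time read. That requires an enrolled preterm child whose shifted time crosses the time being read. The documents give no count of preterm infants.

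Three stronger conclusions are not supported:

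- That the curve and the proportions will disagree. They may, under the conditions just stated.
- That the result will be out of line with the literature. This assumes that published ages are chronological, which the documents do not state.
- That an early death could drop out of the estimate. Subtracting 2.30 from a death at 2.0 months does give −0.30, but the case is extreme and the documents do not say how such a value would be handled.

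**What to change.** Delete the adjustment sentence from SAP 9.4.2. Add that time to death, censoring time and milestone ages are chronological, counted from the date of birth, for every child including those born preterm.

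If a corrected-age analysis is wanted, specify it as a labelled sensitivity analysis: the rule, the source of gestational age and the handling of censored children. It should not replace the chronological analysis.

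The cost is one sentence removed and one added in the SAP. No new data are needed, and the printed formula already gives the chronological time to death. Only the optional sensitivity analysis would need gestational age.
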